#### 8.1.3 Other study parameters (if applicable)

Age, gender, body height (for calculating BMI), cigarette smoking, highest education level, family history of diabetes; for women, history of gestational diabetes.

### 8.2 Randomisation, blinding and treatment allocation

- Subjects will be stratified to sex and fasting blood glucose group (between 5.6 and 6.9 mmol/L or between 5.0 and 5.6 mmol/L) and within these strata subjects will be randomly assigned to arm A or B. Randomisation will be performed using a random number generator by a researcher unrelated to the study. The randomisation code will be broken after data-analysis.

### 8.3 Study procedures

The volunteers will have a pre-study screening before the start of the intervention. This will involve:

- assessment of medical history
- assessment of Diabetes Risk Score (kijkopdiabetes.nl)
- assessment of regular fibre intake measured with a specific food frequency questionnaire
- measuring height, weight, waist circumference
- measuring fasting glucose from finger prick

For the timing of the procedure, see Table 1 in the Chapter Study Design. For logistic reasons subjects will be divided in two groups, starting their treatment period on two consecutive days. For both series the first day of treatment will be specified as Day 01.

During the main part of the intervention the subjects will consume 30 grams of WF fibre or 16 grams of placebo per day, for 21 consecutive days. Before starting, a fasting venous blood sample (total 30ml) will be taken to determine fasting blood glucose and insulin concentrations, and body weight and waist circumference will be measured. Subjects are asked to provide a stool sample for microbiota determination. For this, the participants will receive a home sampling kit with instructions from the WU Laboratory of Microbiology. Also a continuous blood glucose meter will be placed. Also a fasting breath sample will be obtained.

A run in period of 2 weeks on 15 gram WF fibre or 8 grams of placebo will precede the trial to avoid gastro-intestinal discomfort. After that, and before starting the main phase of the intervention, another stool sample will be asked for.

After 21 days of intervention with the full dose, a fasting blood sample, a stool sample, a breath sample and data on body composition will be obtained. After another 14 days of wash-out a final stool sample will be obtained. During the 49 days study period (2+3+2 weeks of run-in, intervention and wash-out resp.) a diary on abdominal side effects will be kept.

Compliance will be assessed by asking subjects to return unused and opened non-empty sachets.

#### 8.4 Details on measurements

All measurements will be done using validated methods developed for their purpose, and by experienced laboratories.

During screening, capillary blood sampling will be used for determination of fasting blood glucose using HemoCue B-glucose device (HemoCue AB, Ängelholm, Sweden).

During the intervention fasting insulin and fasting glucose will be measured in serum and NaF-plasma, respectively, as obtained by venepuncture, by Laboratory Clinical Chemistry of ZGV Hospital Ede. HOMA-ir will be calculated from fasting glucose and insulin levels using software from Matthews et al. (1985) (<https://www.dtu.ox.ac.uk/homacalculator>). For GLP-1 and PYY measurements blood will be collected in tubes with aprotinin.

Abbott's FreeStyle Libre Flash will be used as CGM (see Bolinder et al, 2016). It includes a very tiny glucose sensor worn under the skin and connected to a water resistant, plastic on-body patch the size of a coin. The sensor remains inserted for max. 14 days and does not require fingerstick calibrations. The sensor can be inserted by the subject

him/her-self. To obtain readouts a reader device is being used which is held near the sensor patch. The results (glucose value, trend and graph of last eight hours) can be seen immediately (in this case the screen will be covered for the participants) or downloaded to PC software. EasyGV software will be used to assess measures of glycemic variability (Hill et al., 2011) (m-value, mean amplitude of glycaemic excursions, lability index, average daily risk range, j-Index, low blood glucose index and high blood glucose index, continuous overall net glycemic action, mean of daily differences, glycaemic risk assessment diabetes equation, mean average glucose).

Body weight will be measured to the nearest 0.1 kg. Body height will be measured to the nearest 0.1 cm. Waist circumference will be measured to the nearest 0.5 cm.

Microbiota analysis will be performed by the WU Laboratory of Microbiology on faecal samples essentially as described previously (Salonen et al., 2014) with the modification that extracted DNA will be subject to next generation 16S rRNA and/or metagenomic sequencing as described (Korpela et al 2016; Li et al 2016).

Breath hydrogen is an end product of fermentation in the large bowel and correlates strongly with colonic fermentation. Hydrogen will be measured by collecting breath samples using 250-ml sample holding bags (Quintron, Milwaukee, USA). Samples will be collected during the study visits in the fasting state. Breath hydrogen will be measured the collected breath samples using Quintron Microanalyzer (Quintron Instruments, Milwaukee, US).

Serum will be stored at -80°C until laboratory analyses. The analyses for fasting GLP-1/PYY and SCFA will be done later, the laboratory has not yet been identified.

## **8.5 Withdrawal of individual subjects**

Subjects may discontinue the trial at any moment without the obligation to state the reason for discontinuation. Subjects may be withdrawn from the study by the principal investigator if they do not comply with the rules and regulations of the study. Subjects may be withdrawn from the study by the medical supervisor in case of reported serious adverse events or in case of other medical/social/psychological events as evaluated by the medical investigator and discussed with the principal investigator.

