### **8.5.1 Specific criteria for withdrawal (if applicable)**

Not applicable

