## **8.6 Replacement of individual subjects after withdrawal**

Subjects not completing the study for any reason will be considered as drop-outs and will not be replaced.

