## **8.7 Follow-up of subjects withdrawn from treatment**

Not applicable.

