### **8.8 Premature termination of the study**

Since all ingredients of the products are suitable for human consumption and are microbiologically safe, we do not expect any negative or adverse events. However, a very high intake or an unusual high dose of dietary fibres may result in uncomfortable though harmless effects as increased flatulence or bloating. Research has shown that these adverse events are highly variable among people. Participants will be notified on these side effects in the participant information. The study will be terminated immediately if there would be another problem with the products when they appear to be harmful to the participants' health. In that case, all participants will be informed about this as soon as possible. Furthermore, we will inform the accredited METC.

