### 10.1 Primary study parameter(s)

Fasting insulin, and related/correlated HOMO-ir, derived from fasting glucose and fasting insulin (Matthews et al., 1985), will be analysed as continuous outcome variables. Descriptive statistics will be used to summarize values and changes from baseline by visit. The main analysis will consist of ANCOVA with end-line fasting insulin (or HOMA-ir) as outcome variable, treatment group as factor, and baseline insulin (of HOMA-ir) and age-group, BMI group and gender as covariates. The differences in least square means between the treatment groups and corresponding 95% confidence interval and p-value will be presented.

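### Subjects withdrawn for non-compliance before Day 22 lose their only post-baseline insulin sample, because 8.5 permits removal from the study and 8.7 provides no follow-up

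*Protocol*

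**What the plan says.** Withdrawal and follow-up are covered in four short sections of the protocol.

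- Section 8.5: "Subjects may be withdrawn from the study by the principal investigator if they do not comply with the rules and regulations of the study". The wording concerns leaving the study, not only stopping the product. The same section separately covers a subject's own decision to leave and withdrawal by the medical supervisor.
- Section 8.5.1, which would hold specific withdrawal criteria, is marked not applicable.
- Section 8.6: "Subjects not completing the study for any reason will be considered as drop-outs and will not be replaced".
- Section 8.7, headed "Follow-up of subjects withdrawn from treatment", is marked not applicable.

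On measurement, Table 1 schedules fasting blood at Day -17 and Day 22 only. Section 8.3 confirms the second of these: "After 21 days of intervention with the full dose, a fasting blood sample" is to be obtained. Compliance is judged from sachets: "Compliance will be assessed by asking subjects to return unused and opened non-empty sachets". Table 1 places that check at Day 1 and Day 22, and no cut-off is given.

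The primary analysis in section 10.1 is "ANCOVA with end-line fasting insulin (or HOMA-ir) as outcome variable, treatment group as factor", adjusted for the baseline value and other covariates.

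**The concern.** Sections 3 and 8.3 put each arm on its own product during run-in, at a reduced amount. Allocation therefore precedes run-in, and any subject removed during or after it is removed after randomisation. Such a subject misses Day 22, which is the only occasion on which the outcome of the ANCOVA is measured.

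Randomisation protects a comparison of everyone allocated. It does not protect a comparison of those still present three weeks into the full amount, if staying is related both to the product and to the outcome. The protocol gives a reason why staying might depend on the product. Section 3 introduces the run-in to limit possible gastrointestinal effects of WF, section 8.8 says that "a very high intake or an unusual high dose of dietary fibres may result in uncomfortable though harmless effects as increased flatulence or bloating", and section 11.3 says such effects sometimes occur. A subject with these complaints may take less product, and 8.5 then allows removal.

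This is a matter for the protocol and not only for the SAP. An SAP can define an analysis set or an imputation model, but it cannot supply a blood sample that was never taken.

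**Working it through.** **Inputs.** From section 4.5: SD of change 37 pmol/L; planned reduction 29 pmol/L on WF against 0 on control; two-sided alpha 5%; 27 evaluable subjects per arm; 10% drop-out; 30 randomised per arm. The documents give no expected loss by arm, so the splits below are assumptions.

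**The plan's own figures.** A two-sample t-test (noncentral t) gives 20 per arm at an effect size of 0.92 (power 80.9%) and 27 per arm at 0.78 (power 80.3%). Then 54 / (1 - 0.10) = 60. All three stated sizes (40, 54, 60) reproduce. The step from 54 to 60 also shows that the plan counts drop-outs as lost to the analysis. It restores numbers, not comparability.

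**Illustration 1: completers against all randomised.** Assume that retained WF subjects show the full 29 pmol/L, lost WF subjects would have shown no benefit, and control shows 0. The all-randomised difference is 29 x (share of WF retained). The expected loss is 10% of 60 = 6 subjects.

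- Equal split, 3 of 30 lost on WF: 29 x 27/30 = 26.1 pmol/L, which is 2.9 below the completer value.
- All 6 on WF, 6 of 30 lost: 29 x 24/30 = 23.2 pmol/L, which is 5.8 below.

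This is the gap between two target quantities. It is not selection bias: with no true effect, both are zero.

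**Illustration 2: selection with no true effect.** Assume that losses occur only on WF, with lost fraction q, and that lost subjects' insulin change is k SD worse than that of retained subjects. Setting the whole-arm mean to zero gives a retained-arm mean of -q x k x 37, an apparent WF benefit of q x k x 37. The rejection rate is that of a two-sided 5% t-test with SD 37.

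| WF lost | k | Apparent benefit (pmol/L) | Rejection rate |
|---|---|---|---|
| 3 of 30 | 0.5 | 0.10 x 0.5 x 37 = 1.85 | 5.4% |
| 3 of 30 | 1.0 | 0.10 x 1.0 x 37 = 3.7 | 6.6% |
| 6 of 30 | 0.5 | 0.20 x 0.5 x 37 = 3.7 | 6.5% |
| 6 of 30 | 1.0 | 0.20 x 1.0 x 37 = 7.4 | 11.1% |

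If q and k are the same in both arms, the two shifts cancel. If the worse subjects are lost from control, or the better ones from WF, the sign reverses. The table shows what selective loss could do, not what will happen.

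**The case against.** Several points on the other side stand.

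- Removal under 8.5 is permitted, not required, and its ground is wider than missed sachets. No text ties the sachet check or intolerance to removal. A poor complier who attends Day 22 stays in the ANCOVA, because 10.1 excludes nobody.
- Section 8.7 may be a template entry meaning that nobody foresaw a subject stopping the product while remaining in the study. Nothing says that such a subject must leave.
- The protocol plays down intolerance. Section 8.8 expects no adverse events and speaks of very high or unusual intakes. Section 11.3 places total intake below the level it links to discomfort. The reduced run-in and the payment in proportion to time in study (section 11.6) may also limit loss.
- The analysis set may be defined in an SAP that is not at hand, so its absence from 10.1 is no fault.

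A reader might go further and infer that the ANCOVA is bound to become an analysis of tolerant completers that favours WF, or that loss will probably be heavier on WF. The documents support neither: they give gastrointestinal effects as a possibility and say nothing about loss by arm.

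A reader might also take the ratios 29/26.1 = 1.11 and 29/23.2 = 1.25 as an expected bias of 11 to 25% from loss mainly on WF. That does not follow. The lower end is an equal split, the upper end puts every loss on one arm, and both assume no benefit at all in those lost.

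Finally, a reader might suspect that staff remove subjects knowing their product. The design is single-blind, and under section 6.6 the research team packs the products. Section 8.2, however, has an unrelated researcher randomise and keeps the code until after analysis. Staff knowledge is possible but not shown.

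None of this answers the central point, that a subject removed before Day 22 has no outcome and that the protocol makes no provision to obtain one.

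**Conclusion.** The point holds in limited form. Sections 8.5, 8.5.1, 8.6 and 8.7 together permit discretionary removal of randomised subjects for non-compliance, with no provision to measure them afterwards. With a single post-baseline sample, each subject removed before Day 22 is lost to the primary analysis. That opens the comparison to post-randomisation selection, of unknown direction and size.

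At the planned 10% loss the effect is modest in most of the cases worked through. Under the zero-benefit assumption, the all-randomised difference is 26.1 pmol/L (equal split) or 23.2 pmol/L (all six on WF) against 29 in completers. Partial benefit in those lost would narrow the gap. With no true effect and one-sided loss of three or six WF subjects, the spurious difference is about 2 to 7 pmol/L. This is a cheap improvement to a stated rule, not a flaw that invalidates the trial.

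**What to change.** In sections 8.5 and 8.7, distinguish a subject who stops the product from one who leaves the study. State that non-compliance is not a reason to stop measuring. Invite every randomised subject who still consents, and for whom the medical supervisor has no objection, to the existing Day 22 visit for the fasting sample, and analyse these subjects in the arm to which they were allocated. If the SAP already defines the analysis set, check that it agrees. The subject's right to leave, the medical supervisor's role and all decisions on when to stop the product stay as they are.

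The cost is protocol wording and a few visits by subjects no longer taking the product. The estimate will include poor compliers and may be smaller. Under the zero-benefit assumption (unadjusted t-test, SD held at 37), following all 60 gives power of 76.6% at 26.1 pmol/L and 66.6% at 23.2. Completers at 29 would give 80.7% (27 against 27) and 80.2% (24 against 30). The completer figures are higher because they describe an effect in a selected group, so they are no argument against collecting the sample.

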### **8.5.1 Specific criteria for withdrawal (if applicable)**

Not applicable

## **8.6 Replacement of individual subjects after withdrawal**

Subjects not completing the study for any reason will be considered as drop-outs and will not be replaced.

## **8.7 Follow-up of subjects withdrawn from treatment**

Not applicable.

### **8.8 Premature termination of the study**

Since all ingredients of the products are suitable for human consumption and are microbiologically safe, we do not expect any negative or adverse events. However, a very high intake or an unusual high dose of dietary fibres may result in uncomfortable though harmless effects as increased flatulence or bloating. Research has shown that these adverse events are highly variable among people. Participants will be notified on these side effects in the participant information. The study will be terminated immediately if there would be another problem with the products when they appear to be harmful to the participants' health. In that case, all participants will be informed about this as soon as possible. Furthermore, we will inform the accredited METC.

## 9. SAFETY REPORTING

### 9.1 Section 10 WMO event

In accordance to section 10, subsection 4, of the WMO, the sponsor will suspend the study if there is sufficient ground that continuation of the study will jeopardise subject health or safety. The sponsor will notify the accredited METC without undue delay of a temporary halt including the reason for such an action. The study will be suspended pending further review by the accredited METC. The investigator will take care that all subjects are kept informed.

### 9.2 AEs, SAEs and SUSARs

#### 9.2.1 Adverse events (AEs)

Adverse events are defined as any undesirable experience occurring to a subject during the study, whether or not related to the experimental diets. All adverse events reported spontaneously by the subject or observed by the investigator or his staff will be recorded.

#### 9.2.2 Serious adverse events (SAEs)

As of 1 January 2010, submitters of investigator-initiated research are required to report serious adverse events through the web-portal Toetsing Online within 15 days. This requirement also applies for studies not involving a medicinal product.

A serious adverse event is any untoward medical occurrence or effect that at any dose:

- results in death;
- is life threatening (at the time of the event);
- requires hospitalisation or prolongation of existing inpatients' hospitalisation;
- results in persistent or significant disability or incapacity;
- is a congenital anomaly or birth defect;
- Any other important medical event that may not result in death, be life threatening, or require hospitalization, may be considered a serious adverse experience when, based upon appropriate medical judgement, the event may jeopardize the subject or may require an intervention to prevent one of the outcomes listed above.

The sponsor will report the SAEs through the web portal Toetsing Online to the accredited METC that approved the protocol, within 15 days after the sponsor has first knowledge of the serious adverse events.

SAEs that result in death or are life threatening should be reported expedited. The expedited reporting will occur not later than 7 days after the responsible investigator has first knowledge of the adverse event. This is for a preliminary report with another 8 days for completion of the report.

#### 9.2.3 Suspected unexpected serious adverse reactions (SUSARs)

Not applicable

### **9.3 Annual safety report**

In addition to the expedited reporting of SUSARs, the sponsor will submit, once a year throughout the clinical trial, a safety report to the accredited METC, competent authority, and competent authorities of the concerned Member States.

This safety report consists of:

- a list of all suspected (unexpected or expected) serious adverse reactions, along with an aggregated summary table of all reported serious adverse reactions, ordered by organ system, per study;
- a report concerning the safety of the subjects, consisting of a complete safety analysis and an evaluation of the balance between the efficacy and the harmfulness of the product under investigation.

### **9.4 Follow-up of adverse events**

All AEs will be followed until they have abated, or until a stable situation has been reached. Depending on the event, follow up may require additional tests or medical procedures as indicated, and/or referral to the general physician or a medical specialist.

SAEs need to be reported till end of study within the Netherlands, as defined in the protocol.

The follow-up of AE's will also be reported in the annual progress report.

### **9.5 Data Safety Monitoring Board (DSMB) / Safety Committee**

Not applicable.

## 10. STATISTICAL ANALYSIS

The statistical analyses will be carried out by SPSS (Version23; 2015, IBM SPSS Statistics) or a comparable software program. Statistical test will be done two-sided with a significance level of 5%. Normality will be checked for all continuous outcome variables by inspecting Q-Q plots.

For the descriptive analyses results will be presented as mean  $\pm$  SD, or median and interquartile range, or percentage, depending on their distribution.

### 10.1 Primary study parameter(s)

Fasting insulin, and related/correlated HOMO-ir, derived from fasting glucose and fasting insulin (Matthews et al., 1985), will be analysed as continuous outcome variables. Descriptive statistics will be used to summarize values and changes from baseline by visit. The main analysis will consist of ANCOVA with end-line fasting insulin (or HOMA-ir) as outcome variable, treatment group as factor, and baseline insulin (of HOMA-ir) and age-group, BMI group and gender as covariates. The differences in least square means between the treatment groups and corresponding 95% confidence interval and p-value will be presented.

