## 8. METHODS

### 8.1 Study parameters/endpoints

#### 8.1.1 Main study parameter/endpoint

Fasting insulin and HOMA-ir (homeostatic model assessment of insulin resistance, derived from fasting insulin and fasting glucose levels).

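### The primary ANCOVA omits fasting-glucose group, one of the two stratification factors; adding it is a one-sentence change with a small gain in reported precision or power

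*Protocol*

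**What the plan says.** Section 8.2 of the protocol sets out the allocation: "Subjects will be stratified to sex and fasting blood glucose group", the glucose groups being 5.0-5.6 and 5.6-6.9 mmol/L, and "within these strata subjects will be randomly assigned to arm A or B". On the mechanism it adds only this: "Randomisation will be performed using a random number generator by a researcher unrelated to the study". No blocking or other means of forcing balance is described.

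Section 10.1 fixes the main analysis as "ANCOVA with end-line fasting insulin (or HOMA-ir) as outcome variable", with "treatment group as factor, and baseline insulin (of HOMA-ir) and age-group, BMI group and gender as covariates". Glucose group is not in that list. Age and BMI, which are not stratification factors, are in it as groups.

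HOMA-ir, the other primary outcome, is "derived from fasting insulin and fasting glucose levels" (section 8.1.1), so its baseline value already carries glucose information. Section 10.2 analyses the continuous secondary outcomes in the same manner as the primary ones, so the covariate list carries over.

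**The concern.** A trial is normally analysed by the factors it was stratified on. Forced balance on a prognostic factor removes that factor's contribution to the difference between arms. A model without the factor still counts that contribution as residual noise, so its standard error overstates the uncertainty, the confidence interval is too wide and the test is conservative. If balance is not forced, the standard error is correct, but a prognostic variable that is already recorded goes unused.

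The covariate list is stated in the protocol, so this is not a detail waiting for an analysis plan. The design also has little slack: the 60 randomised subjects cover 54 evaluable at 80% power with exactly 10% drop-out. A secondary matter is that age and BMI, both available as continuous values, enter as groups and so lose some of their prognostic information.

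**Working it through.** **The plan's own figures.** Inputs from section 4.5: standardised effects of 0.92 and 0.78, SD of change 37 pmol/L, 80% power, two-sided 5%, 10% drop-out.

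- 2.45/√7 = 0.926 (stated as 0.92); 34/37 = 0.919; 29/37 = 0.784.
- The noncentral t distribution gives 20 per arm (power 80.9%) at 0.92 and 27 per arm (power 80.3%) at 0.78.
- 54/0.9 = 60.

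All stated sizes reproduce. They rest on a two-sample t-test without covariates, so the choice of ANCOVA covariates does not alter them.

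**Assumptions.** The protocol gives no prognostic strength for glucose group, age or BMI. Let R² be the share of outcome variance left after the baseline value that a factor explains. Assumed ranges: 2-10% for glucose group, 2-5% each for age and BMI.

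**Glucose group, by formula.** With exact balance within strata, the reported standard error exceeds the true one by a factor 1/√(1−R²):

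- R² 2%: 1/√0.98 = 1.010
- R² 5%: 1/√0.95 = 1.026
- R² 10%: 1/√0.90 = 1.054

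**Glucose group, by simulation.** The formula assumes perfect balance, so the section 10.1 model was also simulated: 54 evaluable subjects, 20,000 runs per setting, age and BMI split at the median, sex and glucose groups of equal expected size, covariates independent. Allocation was either in permuted blocks of four within sex-by-glucose strata or unrestricted. Standard error (SE), SD of the estimate and type I error below refer to the protocol's model with no treatment effect. Power is at a standardised difference of 0.78.

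| Allocation | Glucose R² | Age, BMI R² each | Mean reported SE | True SD of estimate | Type I error | Power, protocol model | Plus glucose group | Plus continuous age and BMI |
|---|---|---|---|---|---|---|---|---|
| Blocked | 2% | 2% | 0.2758 | 0.2752 | 5.0% | 79.1% | 79.3% | 80.2% |
| Blocked | 5% | 5% | 0.2707 | 0.2649 | 4.3% | 80.7% | 82.2% | 83.9% |
| Blocked | 10% | 5% | 0.2707 | 0.2580 | 4.0% | 81.5% | 84.5% | 86.0% |
| Unrestricted | 2% | 2% | 0.2810 | 0.2795 | 4.8% | 77.3% | 77.3% | 77.9% |
| Unrestricted | 5% | 5% | 0.2752 | 0.2779 | 5.1% | 78.7% | 79.9% | 81.4% |
| Unrestricted | 10% | 5% | 0.2754 | 0.2763 | 5.0% | 79.0% | 82.5% | 83.9% |

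The difference of 0.78 is applied to the variation left after baseline, so the gains between models matter more than the absolute power levels. The Monte Carlo error of each power figure is about √(0.8 × 0.2/20,000) = 0.3 points.

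- *Blocked.* Reported SE over true SD: 0.2758/0.2752 = 1.002, 0.2707/0.2649 = 1.022, 0.2707/0.2580 = 1.049. The estimate itself hardly improves when glucose group is added: at R² 10% its SD goes from 0.2580 to 0.2565, or 0.6%. The loss lies in the reported SE.
- *Unrestricted.* Reported SE and true SD agree within about 1%. Here the loss is real precision: at R² 10% the SD is 0.2763 without glucose group and 0.2636 with it, a ratio of 1.048.
- *Power.* Adding glucose group gains about 0 to 3.5 points over the six settings.

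**Age and BMI as groups.** A median split of a normal covariate keeps 2/π = 64% of the variance it explains; tertiles keep 79%. The SE ratio against a continuous term is √((1 − k·R²)/(1 − R²)), where k is the share kept. For a median split (k = 0.637) it is 1.004, 1.010 and 1.020 at R² of 2, 5 and 10%; for tertiles (k = 0.793) it is 1.002, 1.005 and 1.011. In the table the last step adds 0.6 to 1.7 power points. Both changes together add 0.6 to 4.9.

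**The case against.** The strongest reply is that the consequence is conditional. The standard error is mis-stated only if allocation is forced to balance within strata and glucose group predicts the outcome after the covariates already in the model. Section 8.2 mentions only a random number generator, and no figure in the protocol supports any particular prognostic strength. At R² of 2% there is no measurable mismatch even with blocking. This stands. A reader might infer from the omission that the standard errors do not match the randomisation; the protocol does not support that as a flat statement. Forced balance is nonetheless the more natural reading, since stratifying without it has no effect and section 3 plans two arms of exactly 30. Under the other reading the adjustment still helps.

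The reply is also right about HOMA-ir: its baseline is computed partly from fasting glucose, so the glucose group should add less there. That outcome was not simulated separately.

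On grouping, three stronger claims are tempting and fail:

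- Unstated cut-points leave room for choice after the data are seen. Group definitions are commonly left to the analysis plan, which is not at hand, so their absence is no fault here.
- Grouping wastes degrees of freedom. A two-level group uses one, the same as a linear term.
- Over a third of the covariate information is lost. The 64% assumes a median split, which the protocol does not state, and even then the standard error moves by 2% or less per covariate.

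Continuous terms also assume linearity, which groups do not.

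**Conclusion.** The omission is real: one of the two stratification factors is missing from a covariate list that the protocol fixes, and no reason is given. Its effect is small and takes one of two forms. With balance within strata, the reported standard error is about 0-5% too large and type I error falls to between 5.0% and 4.0%, with almost no loss in the true precision of the estimate. With unrestricted allocation, the standard error is valid and some power is lost if glucose group is prognostic. Both rest on an assumed residual R² of 2-10% for glucose group.

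A reader might take the mismatch to mean that the primary test is invalid or too liberal. It is not: no setting showed false-positive inflation, and the sample size is unaffected. Entering age and BMI as groups is a lesser matter of preference with a small cost. Severity: minor.

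**What to change.** In section 10.1, add the fasting-glucose stratum to the ANCOVA, using the group recorded at randomisation from the screening measurement rather than one re-derived from the later venous sample. This costs one degree of freedom and one sentence, and uses data already collected. Section 10.2 needs no separate rewrite, because it already refers back to the primary method. It would help to state in section 8.2 whether, and how, balance within strata is achieved.

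Secondarily, enter age and BMI as continuous covariates, accepting the linearity assumption, or give the reason for grouping them. Make the change before the randomisation code is broken.
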